4.1 Study/project specific decisions

For each study (or project) various issues need to be addressed and specified in the protocol or RAP documentation. Any deviations from protocol must be discussed and defined at the latest in the RAP documentation.

The proposed primary analysis and potential sensitivity analyses should be discussed and agreed with the health authorities and documented in the protocol (or at the latest in the RAP documentation before database lock).

4.2 End of treatment phase completion

Patients **may** voluntarily withdraw from the study treatment or may be taken off the study treatment at the discretion of the investigator at any time. For patients who are lost to follow-up, the investigator or designee should show "due diligence" by documenting in the source documents steps taken to contact the patient, e.g., dates of telephone calls, registered letters, etc.

The end of treatment visit and its associated assessments should occur within 7 days of the last study treatment.

Patients may discontinue study treatment for any of the following reasons:

- Adverse event(s)
- Lost to follow-up
- Physician decision
- Pregnancy
- Protocol deviation
- Technical problems
- Subject decision
- Death
- Progressive disease
- Study terminated by the sponsor
- Non-compliant with study treatment
- No longer requires treatment
- Treatment duration completed as per protocol (optional, to be used if only a fixed number of cycles is given)

4.3 End of post-treatment follow-up (study phase completion)

End of post-treatment follow-up visit will be completed after discontinuation of study treatment and post-treatment evaluations but prior to collecting survival follow-up.

Patients may provide study phase completion information for one of the following reasons:

- Adverse event
- Lost to follow-up
- Physician decision
- Pregnancy
- Protocol deviation
- Technical problems
- Subject decision
- Death
- New therapy for study indication
- Progressive disease
- Study terminated by the sponsor

4.4 Medical validation of programmed overall lesion response

As RECIST is very strict regarding measurement methods (i.e. any assessment with more or less sensitive method than the one used to assess the lesion at baseline is considered UNK) and not available evaluations (i.e. if any target or non-target lesion was not evaluated the whole overall lesion response is UNK unless remaining lesions qualified for PD), these UNK assessments may be re-evaluated by clinicians at Novartis or external experts. In addition, data review reports will be available to identify assessments for which the investigators' or central reader's opinion does not match the programmed calculated response based on RECIST criteria. This may be queried for clarification. However, the investigator or central reader's response assessment will never be overruled.

If Novartis elect to invalidate an overall lesion response as evaluated by the investigator or central reader upon internal or external review of the data, the calculated overall lesion response at that specific assessment is to be kept in a dataset. This must be clearly documented in the RAP documentation and agreed before database lock. This dataset should be created and stored as part of the 'raw' data.

Any discontinuation due to 'Disease progression' without documentation of progression by RECIST criteria should be carefully reviewed. Only patients with documented deterioration of symptoms indicative of progression of disease should have this reason for discontinuation of treatment or study evaluation.

4.5 Programming rules

The following should be used for programming of efficacy results:

4.5.1 Calculation of 'time to event' variables

Time to event = end date - start date + 1 (in days).

When no post-baseline tumor assessments are available, the date of randomization/start of treatment will be used as end date (duration = 1 day) when time is to be censored at last tumor assessment, i.e. time to event variables can never be negative.

4.5.2 Incomplete assessment dates

All investigation dates (e.g. X-ray, CT scan) must be completed with day, month and year.

If one or more investigation dates are incomplete but other investigation dates are available, this/these incomplete date(s) are not considered for calculation of the assessment date (and assessment date is calculated as outlined in [Section 3.2.7](#)). If all measurement dates have no day recorded, the 1st of the month is used.

If the month is not completed, for any of the investigations, the respective assessment will be considered to be at the date which is exactly between previous and following assessment. If a previous and following assessment is not available, this assessment will not be used for any calculation.

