7.2 Assessment types

7.2.1 Efficacy assessments

Tumor assessment and response will be evaluated according to RECIST (Version 1.1) (Protocol Post-text Supplement: 1). All radiologic assessments must be performed within a +/- 7 day window of the visit.

Patients should have either at least one lesion that can be measured as per RECIST criteria OR have bone lesions: lytic or mixed (lytic + sclerotic) in the absence of measurable disease OR have non-measurable disease.

For patients with measurable disease at screening (as per RECIST criteria), tumor progression will be evaluated every 12 weeks until progression or End of study, whichever is first (according to the RECIST 1.1 criteria). All tumor evaluations performed routinely in addition to the above mentioned will be evaluated and documented according to RECIST 1.1 as well. All patients being discontinued from the study for disease progression must have their progression documented using the criteria specified in RECIST 1.1.

Bone scans must be performed at screening within 56 days before C1D1. Positive areas on bone scans must be assessed by X-ray or CT scan with bone windows, prior to C1D1 and should continue to be assessed using the same modality (X-ray or CT scan) every 12 weeks until progression or End of study. Additional bone scans should be performed if clinically indicated. Abnormalities found on subsequent bone scans must be confirmed by X-ray or CT scan. Bone scans may be replaced by whole body CT, provided that this is local standard. The whole-body CT must be performed within a +/- 7 days window of the visit.

Color photography, including a metric ruler to estimate the size of the lesion, must be acquired for all skin lesions present at baseline. These should be followed throughout the study according to the schedule outlined in Table 7-1.

All patients being discontinued from the study for other reasons than tumor progression (or death) should be scheduled for tumor evaluation at 12 week intervals after discontinuation until LPLV occurs.

The same method of assessment and the same technique should be used to characterize each identified and reported lesion at baseline for each study tumor assessment after start of study treatment.

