4.5.3 Incomplete dates for last known date patient alive or death

All dates must be completed with day, month and year. If the day is missing, the 15th of the month will be used for incomplete death dates or dates of last contact.

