5.4 Imputation rules

5.4.1 Incomplete assessment dates

All investigation dates (e.g. X-ray, CT scan) must have been completed with day, month and year.

If one or more investigation dates was incomplete but other investigation dates were available, this/these incomplete date(s) was/were not considered for calculation of the assessment date (and assessment date was calculated as outlined in Section 3.2.7). If all measurement dates had no day recorded, the 1st of the month is used.

If the month was not completed, for any of the investigations, the respective assessment was considered to be at the date which is exactly between previous and following assessment. If a previous and following assessment was not available, this assessment was not used for any calculation.

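### The missing-month rule can lose or delay a progression recorded at the last tumour assessment, and the day-15 imputation for death and last contact has no lower bound

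*Protocol*

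**What the plan says.** Protocol Appendix 2 section 4.5.2 requires complete investigation dates and then sets fallbacks.

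- Second paragraph: "If one or more investigation dates are incomplete but other investigation dates are available, this/these incomplete date(s) are not considered". The assessment is then dated from the complete dates. If every date lacks its day, the 1st of the month is used.
- Third paragraph: "If the month is not completed, for any of the investigations, the respective assessment will be considered to be at the date" midway between the previous and the following assessment. It ends: "If a previous and following assessment is not available, this assessment will not be used for any calculation".

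SAP 5.4.1 carries both paragraphs over, ending: "If a previous and following assessment was not available, this assessment was not used for any calculation".

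On the scan schedule, Protocol 7.2.1 says, for patients with measurable disease, that "tumor progression will be evaluated every 12 weeks until progression or End of study". Protocol 7.2.1.1 adds a scan at symptomatic progression for patients treated beyond radiologic progression. SAP 2.7.2 censors PFS without an event at the last adequate tumour assessment.

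SAP 5.1 takes progression from several fields, including the end-of-treatment page. It offers two dates for it: the date of clinically symptomatic progress, or the date of the evaluation showing PD or a new lesion.

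For deaths and last contacts, Appendix 2 section 4.5.3 says: "If the day is missing, the 15th of the month will be used for incomplete death dates or dates of last contact". SAP 5.4.2 has the same rule, and neither sets a lower bound. Appendix 2 section 4.5.1 computes time to event as end minus start plus one day and concludes that "time to event variables can never be negative".

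**The concern.** There are three linked defects.

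1. **Terminal assessments.** The midpoint needs a following assessment, and a progression scan often has none. Excluding a progression-free patient's last scan only moves a censoring date. Excluding a progression scan removes the event or leaves it to be picked up later. For PFS and duration of response the effect therefore runs towards longer times.
2. **Conflicting triggers.** The second paragraph of section 4.5.2 sets an incomplete date aside when complete ones exist. The third is triggered by a missing month for any one investigation. SAP 5.1 dates progression by the evaluation, while SAP 5.4.1 may exclude that same evaluation from every calculation. Two programmers could produce different PFS data from the same records.
3. **Unbounded day-15 rule.** An imputed death or last contact can fall before an event or contact already on record, or before treatment start. The SAP does set bounds for other imputed dates: study treatment (5.4.5), adverse events (5.4.6), concomitant medication (5.4.7) and prior and post antineoplastic therapies (5.4.7.1, 5.4.7.2).

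**Working it through.** **Missing-month rule applied to a 12-weekly sequence.** Take SD at weeks 12 and 24 and PD at week 36.

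| Week-36 record | Result under the text |
|---|---|
| No usable month, no later scan | Excluded. The end-of-treatment page may still flag progression, but a purely radiologic PD then has no date unless the evaluation date is used. PFS is censored at week 24 instead of an event at week 36. |
| No usable month, later scan at week 48 (treated beyond progression) | Midpoint (24 + 48)/2 = week 36. The event is kept. |
| CT fully dated, one X-ray without month | Second paragraph: event at the CT date. Third paragraph read literally: excluded. |
| No usable month, but SD instead of PD, no later scan | Only the censoring date moves, from week 36 to week 24. |

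If the dropped PD is the first post-baseline scan, no adequate assessment remains and the patient is censored at 1 day (Appendix 2 section 4.5.1, SAP 5.3.1).

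**Size, by simulation.** Inputs from the documents are 350 and 150 patients (Protocol 10.8), median PFS of 25.3 months first line and 5.5 months previously treated (Protocol 1.2.6), and 12-weekly scans. The assumptions are exponential PFS, 5.5 months for all of cohort B, follow-up spread evenly over 80–130 weeks, and a share q of progression scans with no usable month. Each such scan is dropped and the patient censored one scan earlier, with no rescue by symptomatic progress or death, so these figures lean high for a given q. With q = 0 there are about 303 events, and week-72 PFS is about 48%.

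| q (assumed) | Events lost | Rise in week-72 PFS (points) |
|---|---|---|
| 0.5% | 1.6 | 0.2 |
| 1% | 3.1 | 0.3 |
| 2% | 6.0 | 0.7 |
| 5% | 15.3 | 1.7 |

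**Day-15 rule.** The plan's own case reproduces: when the end date equals the start date, 0 + 1 = 1 day. For a death in the calendar month of first dose, imputed survival is 15 − start day + 1 = 16 − start day:

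- start on the 15th: 1 day
- start on the 16th: 0 days
- start on the 20th: 15 − 20 + 1 = −4 days
- start on the 31st: −15 days

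A negative time needs a start on the 17th or later and death in the same month, so a true death by study day 31 − 17 + 1 = 15. As a generous rate, take the one early death among 334 ribociclib patients in the earlier phase III study (Protocol 1.2.6). That death was at about day 4 + 19 = 23, too late to give a negative time. The expected number in 500 patients is 500 × (1/334) × (15/31) × share of days missing. This gives 0.007 at 1% missing, 0.04 at 5% and 0.14 at 20%, where the missing shares are assumed.

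Disorder among later dates does not need an early death. With PD on the 20th and death on the 28th of the same month, day missing, the death is placed on the 15th, 5 days before the PD. SAP 5.1.3 takes the first of the two dates, so PFS would then end on the 15th.

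**The case against.** The strongest reply is that section 4.5.2 reads as a sequence: set incomplete dates aside if complete ones exist; use the 1st if all days are missing; use the midpoint only if no month is usable. A reader might infer that one X-ray without a month deletes a PD whose CT is fully dated. On that natural reading it does not, and only the wording of the third paragraph suggests it. This stands, and leaves a conflict of wording to repair.

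A reader might also infer that the dropped assessment is usually the progression scan and that progressions vanish. Neither is shown. The last scan is also the censoring scan of every patient without progression; in the illustration the progression scan is last in about 60% of patients overall and 46% first line. Treatment beyond progression can supply the following scan. SAP 5.1 keeps the other flags and the symptomatic-progress date, and a later death can still count. SAP 2.5.1 sends discontinuations for progression without RECIST documentation to data review. So the event may be lost or delayed, but it need not disappear.

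Frequency should be low. Complete dates are mandatory, entry is validated (Protocol 9.3), missing values are queried (Protocol 9.4), and deaths not due to progression are reported as SAEs (Protocol 8.1.1). The non-negativity statement is argued only for times censored at the last tumour assessment, so it makes no reasoned claim about overall survival. All of this limits the size. It does not supply a rule for a terminal assessment without a usable month, or a bound for the day-15 date.

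**Conclusion.** The point holds as a minor defect. When triggered at a terminal PD, the exclusion rule can lose or delay a PFS or duration-of-response event, and these endpoints then read slightly too long. The documents give no missing-date rate, so any size is conditional: at 1–2% of progression scans, about 3–6 of roughly 303 events and 0.3–0.7 points on week-72 PFS, which is a descriptive secondary estimate.

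The documents do not support reading this as a threat to the primary result. PD and unknown both count as no benefit, so CBR barely moves. Rare exceptions run both ways. A patient with non-measurable disease, one NCRNPD and an excluded PD could count as benefit, because SAP 5.1.1 asks for no repeat NCRNPD. Conversely, an excluded week-24 SD could fail the requirement for two SD determinations.

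Nor do they support expecting negative survival times in practice. They are possible under the rule but very unlikely. The likelier fault is a death or last contact placed before a progression or contact in the same month.

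**What to change.** In SAP 5.4.1 and Appendix 2 section 4.5.2:

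- Apply the midpoint or exclusion rule only when no investigation date at that assessment has a usable month.
- Never exclude a terminal assessment with PD. Date it by the recorded evaluation date (SAP 5.1); failing that, by the next scheduled assessment date (Appendix 2 section 3.2.7), which is the last adequate assessment plus 12 weeks.

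In SAP 5.4.2 and Appendix 2 section 4.5.3:

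- Set an imputed death or last-contact date to the later of the 15th and the last documented date known alive, and never before treatment start. The shortest overall survival time is then 1 day instead of −15.

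The cost is a few sentences in the SAP and the protocol appendix, the latter by amendment under Protocol 12.1, and minor programming. No new data are needed.

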4.5.3 Incomplete dates for last known date patient alive or death

All dates must be completed with day, month and year. If the day is missing, the 15th of the month will be used for incomplete death dates or dates of last contact.

4.5.4 Non-target lesion response

If no non-target lesions are identified at baseline (and therefore not followed throughout the study), the non-target lesion response at each assessment will be considered 'not applicable (NA)'.

4.5.5 Study/project specific programming

The standard analysis programs need to be adapted for each study/project.

4.5.6 Censoring reason

In order to summarize the various reasons for censoring, the following categories will be calculated for each time to event variable based on the treatment completion page, the study evaluation completion page and the survival page.

For survival the following censoring reasons are possible:

- Alive
- Lost to follow-up

For PFS and TTP (and therefore duration of responses) the following censoring reasons are possible:

- Ongoing without event
- Lost to follow-up
- Withdraw consent
- Adequate assessment no longer available*
- Event documented after two or more missing tumor assessments (optional, see [Table 3-2](#))
- Death due to reason other than underlying cancer (*only used for TTP and duration of response*)
- Initiation of new anti-cancer therapy

*Adequate assessment is defined in [Section 3.2.7](#). This reason is applicable when adequate evaluations are missing for a specified period prior to data cut-off (or prior to any other censoring reason) corresponding to the unavailability of two or more planned tumor assessments prior to the cut-off date. The following clarifications concerning this reason should also be noted:

- This may be when there has been a definite decision to stop evaluation (e.g. reason="Sponsor decision" on study evaluation completion page), when patients are not followed for progression after treatment completion or when only UNK assessments are available just prior to data cut-off).
- The reason "Adequate assessment no longer available" also prevails in situations when another censoring reason (e.g. withdrawal of consent, loss to follow-up or alternative anti-cancer therapy) has occurred more than the specified period following the last adequate assessment.
- This reason will also be used to censor in case of no baseline assessment.

5 References (available upon request)

Dent S, Zee (2001) application of a new multinomial phase II stopping rule using response and early progression, *J Clin Oncol*; 19: 785-791

Eisenhauer E, et al (2009) New response evaluation criteria in solid tumors: revised RECIST guideline (version 1.1). *European Journal of Cancer*, Vol.45: 228-47

Ellis S, et al (2008) Analysis of duration of response in oncology trials. *Contemp Clin Trials* 2008; 29: 456-465

FDA Guidelines: 2005 Clinical Trial Endpoints for the Approval of Cancer Drugs and Biologics, April 2005

FDA Guidelines: 2007 Clinical Trial Endpoints for the Approval of Cancer Drugs and Biologics, May 2007

14.3 Appendix 3: Patient reported outcomes

Figure 14-1 EORTC-QLQ-C30

GERMAN

EORTC QLQ-C30 (version 3.0)

Wir sind an einigen Angaben interessiert, die Sie und Ihre Gesundheit betreffen. Bitte beantworten Sie die folgenden Fragen selbst, indem Sie die Zahl ankreuzen, die am besten auf Sie zutrifft. Es gibt keine "richtigen" oder "falschen" Antworten. Ihre Angaben werden streng vertraulich behandelt.

Bitte tragen Sie Ihre Initialen ein:

--	--	--	--

Ihr Geburtstag (Tag, Monat, Jahr):

--	--	--	--	--	--

Das heutige Datum (Tag, Monat, Jahr):

31

--	--	--	--	--

	Überhaupt			
	nicht	Wenig	Mäßig	Sehr
1. Bereitet es Ihnen Schwierigkeiten sich körperlich anzustrengen (z.B. eine schwere Einkaufstasche oder einen Koffer zu tragen)?	1	2	3	4
2. Bereitet es Ihnen Schwierigkeiten, einen längeren Spaziergang zu machen?	1	2	3	4
3. Bereitet es Ihnen Schwierigkeiten, eine kurze Strecke außer Haus zu gehen?	1	2	3	4
4. Müssen Sie tagsüber im Bett liegen oder in einem Sessel sitzen?	1	2	3	4
5. Brauchen Sie Hilfe beim Essen, Anziehen, Waschen oder Benutzen der Toilette?	1	2	3	4

Während der letzten Woche:

	Überhaupt			
	nicht	Wenig	Mäßig	Sehr
6. Waren Sie bei Ihrer Arbeit oder bei anderen tagtäglichen Beschäftigungen eingeschränkt?	1	2	3	4
7. Waren Sie bei Ihren Hobbys oder anderen Freizeitbeschäftigungen eingeschränkt?	1	2	3	4
8. Waren Sie kurzatmig?	1	2	3	4
9. Hatten Sie Schmerzen?	1	2	3	4
10. Mussten Sie sich ausruhen?	1	2	3	4
11. Hatten Sie Schlafstörungen?	1	2	3	4
12. Fühlten Sie sich schwach?	1	2	3	4
13. Hatten Sie Appetitmangel?	1	2	3	4
14. War Ihnen übel?	1	2	3	4
15. Haben Sie erbrochen?	1	2	3	4

Bitte wenden

Während der letzten Woche:

		Überhaupt	nicht	Wenig	Mäßig	Sehr
16. Hatten Sie Verstopfung?			1	2	3	4
17. Hatten Sie Durchfall?			1	2	3	4
18. Waren Sie müde?			1	2	3	4
19. Fühlten Sie sich durch Schmerzen in Ihrem alltäglichen Leben beeinträchtigt?			1	2	3	4
20. Hatten Sie Schwierigkeiten sich auf etwas zu konzentrieren, z.B. auf das Zeitunglesen oder das Fernsehen?			1	2	3	4
21. Fühlten Sie sich angespannt?			1	2	3	4
22. Haben Sie sich Sorgen gemacht?			1	2	3	4
23. Waren Sie reizbar?			1	2	3	4
24. Fühlten Sie sich niedergeschlagen?			1	2	3	4
25. Hatten Sie Schwierigkeiten, sich an Dinge zu erinnern?			1	2	3	4
26. Hat Ihr körperlicher Zustand oder Ihre medizinische Behandlung Ihr Familienleben beeinträchtigt?			1	2	3	4
27. Hat Ihr körperlicher Zustand oder Ihre medizinische Behandlung Ihr Zusammensein oder Ihre gemeinsamen Untemehmungen mit anderen Menschen beeinträchtigt?			1	2	3	4
28. Hat Ihr körperlicher Zustand oder Ihre medizinische Behandlung für Sie finanzielle Schwierigkeiten mit sich gebracht?			1	2	3	4

Bitte kreuzen Sie bei den folgenden Fragen die Zahl zwischen 1 und 7 an, die am besten auf Sie zutrifft29. Wie würden Sie insgesamt Ihren Gesundheitszustand während der letzten Woche einschätzen?

1	2	3	4	5	6	7
sehr schlecht						ausgezeichnet

30. Wie würden Sie insgesamt Ihre Lebensqualität während der letzten Woche einschätzen?

1	2	3	4	5	6	7
sehr schlecht						ausgezeichnet

Figure 14-2: EORTC-QLQ-BR23

EORTC QLQ - BR23

Patienten berichten manchmal die nachfolgend beschriebenen Symptome oder Probleme. Bitte beschreiben Sie, wie stark Sie diese Symptome oder Probleme während der letzten Woche empfunden haben.

Während der letzten Woche:

		Überhaupt			
		nicht	Wenig	Mäßig	Sehr
31.	Hatten Sie einen trockenen Mund?	1	2	3	4
32.	War Ihr Geschmacksempfinden beim Essen oder Trinken verändert?	1	2	3	4
33.	Schmerzten Ihre Augen, waren diese gereizt oder trännten sie?	1	2	3	4
34.	Haben Sie Haarausfall?	1	2	3	4
35.	Nur bei Haarausfall ausfüllen: Hat Sie der Haarausfall belastet?	1	2	3	4
36.	Fühlten Sie sich krank oder unwohl?	1	2	3	4
37.	Hatten Sie Hitzewallungen?	1	2	3	4
38.	Hatten Sie Kopfschmerzen?	1	2	3	4
39.	Fühlten Sie sich wegen Ihrer Erkrankung oder Behandlung körperlich weniger anziehend?	1	2	3	4
40.	Fühlten Sie sich wegen Ihrer Erkrankung oder Behandlung weniger weiblich?	1	2	3	4
41.	Fanden Sie es schwierig, sich nackt anzusehen?	1	2	3	4
42.	Waren Sie mit Ihrem Körper unzufrieden?	1	2	3	4
43.	Waren Sie wegen Ihres zukünftigen Gesundheitszustandes besorgt?	1	2	3	4

Während der letzten vier Wochen:

		Überhaupt			
		nicht	Wenig	Mäßig	Sehr
44.	Wie sehr waren Sie an Sex interessiert?	1	2	3	4
45.	Wie sehr waren Sie sexuell aktiv? (mit oder ohne Geschlechtsverkehr)?	1	2	3	4
46.	Nur ausfüllen, wenn Sie sexuell aktiv waren: Wie weit hatten Sie Freude an Sex?	1	2	3	4

Bitte wenden

GERMAN

Während der letzten Woche:

	Überhaupt			
	nicht	Wenig	Mäßig	Sehr

47. Hatten Sie Schmerzen in Arm oder Schulter?	1	2	3	4
48. War Ihr Arm oder Ihre Hand geschwollen?	1	2	3	4
49. War das Heben oder Seitwärtsbewegen des Arms erschwert?	1	2	3	4
50. Hatten Sie im Bereich der betroffenen Brust Schmerzen?	1	2	3	4
51. War der Bereich Ihrer betroffenen Brust angeschwollen?	1	2	3	4
52. War der Bereich der betroffenen Brust überempfindlich?	1	2	3	4
53. Hatten Sie Hautprobleme im Bereich der betroffenen Brust (z.B. juckende, trockene oder schuppende Haut)?	1	2	3	4
